3.8 DOSING DELAYS AND MODIFICATIONS

Subjects should be followed closely for AEs or laboratory abnormalities that might indicate acalabrutinib- or ACP-319-related toxicity. If a subject experiences a treatment-related DLT or other AE requiring dose modification during the course of

Protocol: ACE-LY-001

therapy, then acalabrutinib, ACP-319, or both drugs should be held, as necessary, until the AE resolves or stabilizes to an acceptable degree.

When restarting treatment, study drugs should be re-introduced in a staggered fashion, after discussion with the medical monitor. If both drugs were withheld, acalabrutinib (at the original or modified dose) should be given alone for at least 7 days, and the subject monitored closely for recurrence of AEs, before adding ACP-319.

3.8.1 Dose Delays

Treatment with acalabrutinib, ACP-319, or both, should be held for any unmanageable, potentially study drug-related toxicity that is Grade ≥3 in severity. Any other clinically important events where dose delays may be considered appropriate by the investigator must be discussed with the medical monitor.

Study drug may be held for a maximum of 28 consecutive days from expected dose due to toxicity. Study treatment should be discontinued in the event of a toxicity lasting >28 days, unless reviewed and approved by the medical monitor.

Note: Temporary withholding of study drug for as little as 7 days can cause a transient worsening of disease and/or of constitutional symptoms, which may not indicate definitive disease progression. Refer to Section 3.12 for more information on assessing disease progression under these circumstances.

3.8.2 Dose Modification and Discontinuation

The actions in Table 3-1 should be taken for any Grade 4 toxicity or unmanageable Grade 3 toxicity. In addition, the actions in Table 3-1 should be taken when modification of the acalabrutinib dose is recommended for specific treatment-related AEs as listed in Table 3-2.

Table 3-1. Dose Modification Actions for Acalabrutinib

| Occurrence | Action |
|------------|---------------------------------------------------------------------------|
| 1st - 2nd | Hold acalabrutinib until recovery to Grade ≤1 or baseline; may restart at |
| | original dose level (100 mg BID) |
| 3rd | Hold acalabrutinib until recovery to Grade ≤1 or baseline; restart at |
| | 100 mg QD |
| 4th | Discontinue acalabrutinib |
| | |

Abbreviations: BID = twice daily; QD = once daily.

Dependent on the subject's initial dose level, subjects who cannot tolerate a rechallenge at the lowest recommended dosages of acalabrutinib and/or ACP-319 should be removed from study treatment.

Protocol: ACE-LY-001

If acalabrutinib and/or ACP-319 are reduced for apparent treatment-related toxicity, the doses need not be re-escalated, even if there is minimal or no toxicity with the reduced doses. However, if the subject tolerates a reduced dose of acalabrutinib and/or ACP-319 for ≥4 weeks then the dose may be increased to the next higher dose level at the discretion of the investigator and after discussion with the medical monitor. Such reescalation may be particularly warranted if further evaluation reveals that the AE that led to the dose reduction was not treatment related.

ACP-319 should be held in subjects with evidence of CMV infection of any grade or viremia (positive PCR or antigen test). ACP-319 may be restarted once the subject is PCR negative, as per investigator discretion. If ACP-319 is resumed, monitor (by PCR or antigen test) for CMV reactivation at least monthly and consider administering pre-emptive CMV therapy. Refer to Section 4.1.24 for monthly CMV testing.

ACP-319 should be held in subjects with suspected *Pneumocystis jirovecii* pneumonia (PJP) infection of any grade. ACP-319 should be discontinued permanently in subjects with active or confirmed PJP infection. Refer to Section 3.10.4 for PJP infection prophylaxis. Whenever possible, any dose adjustment of study drugs should be discussed between the investigator and the medical monitor before implementation. The appropriate clinic staff should dispense the study drug for the new dose level and instruct the subject/caregiver about the change in dose level. Any changes to the dosing regimen must be recorded on the appropriate electronic case report form (eCRF).

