| Grade 3 Severe diarrhea: Increase of ≥7 stools per day over baseline | Provide antidiarrheal (e.g., loperamide). Withhold acalabrutinib until Grade ≤1. Resume at lower dose level (if applicable). Consider addition of anti-inflammatory (e.g., sulfasalazine, budesonide). | Provide antidiarrheal (e.g., loperamide). Withhold ACP-319 until Grade ≤1. Resume at lower dose level (if applicable). Consider addition of anti-inflammatory (e.g., sulfasalazine, budesonide). | | | |
| Grade 4 Life-threatening diarrhea | Provide antidiarrheal (e.g., loperamide). Withhold acalabrutinib until Grade ≤1. May resume at lower dose level (if applicable) or discontinue acalabrutinib at investigator discretion. Consider addition of anti-inflammatory (e.g., sulfasalazine, budesonide). | Discontinue ACP-319 permanently. | | | |
| Hepatic Adverse Events (elevations in ALT, AST, or bilirubin) | | | | | |
| Grade 1 (ALT/AST ≤3 x ULN) (Bilirubin ≤1.5 x ULN) | Maintain current dose level and schedule. Monitor ALT, AST, ALP, and bilirubin at least 1x per week. | Maintain current dose level and schedule. Monitor ALT, AST, ALP, and bilirubin at least 1x per week. | | | |
| Grade 2 (ALT/AST >3-5 x ULN) (Bilirubin >1.5- ≤ 3 x ULN) | | | | | |

Table 3-2. Recommendations for Acalabrutinib and ACP-319 Dose Modifications Based on Type and Severity of Treatment-Related Adverse Events or Laboratory Abnormalities

| | Recommendation | |
|-------------------------------------------------------------|------------------------------------------------------------------------------------------------------------------------------------------------------------------------------------------------------------------------------------------------------------------------------------------------------------|-------------------------------------------------------------------------------------------------------------------------------------------------------------------------------------------------------------------------------------------------------------------------------------------------------------------------------------------------------------------------------------------------------------------------------------------------------------------------------------------|
| NCI CTCAE Grade | Acalabrutinib | ACP-319 |

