| Grade 3 (ALT/AST >5-20 x ULN) (Bilirubin >3-10 x ULN) | Withhold or continue acalabrutinib (at investigator discretion, after discussion with the medical monitor). Monitor ALT, AST, ALP, and bilirubin at least 1x per week. After 7 days if hepatic enzymes appear to be improving and acalabrutinib was withheld, restart acalabrutinib at current dose level. | Withhold ACP-319. Monitor ALT, AST, ALP, and bilirubin at least 1x per week until all abnormalities have returned to Grade ≤1. Recommend treating with high dose oral or IV corticosteroids (at a dosage of 40 mg prednisone or equivalent QD) for at least 48 hours; when all abnormalities have returned to Grade ≤1, recommend tapering steroids over no <4 weeks. Once abnormalities have returned to Grade ≤1, ACP-319 may resume at initial or lower dose level (if applicable). |
| Grade 4 | See recommendations for | Discontinue ACP-319 |
| (ALT/AST >20 x ULN) | Grades 2 or 3 | permanently. |
| (Bilirubin >10 x ULN) | | |
| | | diffuse interstitial pattern or |
| ground-glass opa | cities on chest CT and no d | |
| Grade 1 | Maintain current dose level and schedule. Consider pneumocystis prophylaxis. | Discontinue ACP-319 permanently. |
| Grade 2 | Withhold acalabrutinib until Grade ≤1, consider systemic corticosteroids and pneumocystis treatment. May resume at initial or lower dose level (if applicable) at investigator discretion. | Discontinue ACP-319 permanently. |
| Grade ≥≥3 | Withhold acalabrutinib until Grade ≤1, consider systemic corticosteroids and consider pneumocystis treatment. May resume at lower dose level (if applicable) or discontinue acalabrutinib at investigator discretion. | Discontinue ACP-319 permanently. |

Table 3-2. Recommendations for Acalabrutinib and ACP-319 Dose Modifications Based on Type and Severity of Treatment-Related Adverse Events or Laboratory Abnormalities

| Recommendation | | | | | |
|-----------------|-----------------------------------------------------------------------------------------------------------------------------------------------------------------------------------------------------------------------------------------------------------------------------------------|-------------------------------------------------------------------------------------------------------------------------------------------------------------|--|--|--|
| NCI CTCAE Grade | Acalabrutinib | ACP-319 | | | |
| | Neutropenia | | | | |

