| Grade ≤2 | Maintain current dose level and schedule. | Maintain current dose level and schedule. | | | |
| Grade 3 | Maintain current dose level and schedule. | Maintain current dose level and schedule. Monitor ANC at least 1x per week. | | | |
| Grade 4 | Maintain current dose level and schedule and monitor ANC at least 1x per week. If Grade 4 neutropenia lasts for >7 days (neutrophil growth factors are permitted per ASCO guidelines [Smith et al. 2015b] and use must be recorded on the CRF), modify dose as instructed in Table 3-1. | Withhold ACP-319. Monitor ANC at least 1x per week until ANC ≥0.5 x 10 ⁹ /L, then resume ACP-319 at lower dose level (if applicable). | | | |
| | Thrombocytopenia | 1 | | | |
| Grade ≤2 | Maintain current dose level and schedule. | Maintain current dose level and schedule. | | | |
| Grade 3 | If no significant bleeding, maintain current dose level and schedule. In the presence of significant bleeding, modify dose as instructed in Table 3-1. | Maintain current dose level and schedule. Monitor PLT at least 1x per week. | | | |
| Grade 4 | Modify dose as instructed in Table 3-1. | Withhold ACP-319. Monitor PLT at least 1x per week until PLT ≥25 x 10 ⁹ /L, then resume ACP-319 at lower dose level (if applicable). | | | |
| | Rash | T | | | |
| Grade 1 | Maintain current dose level and schedule. | Maintain current dose level and schedule. | | | |
| Grade 2 | Maintain current dose level and schedule. | Withhold ACP-319 until Grade ≤1, consider systemic corticosteroids. May resume ACP-319 at initial or lower dose (if applicable) at investigator discretion. | | | |

Protocol: ACE-LY-001

Table 3-2. Recommendations for Acalabrutinib and ACP-319 Dose Modifications Based on Type and Severity of Treatment-Related Adverse Events or Laboratory Abnormalities

| | Recommendation | | |
|-------------------------------------|-----------------------------------|---------------------------------|--|
| NCI CTCAE Grade | Acalabrutinib | ACP-319 | |
| | Withhold acalabrutinib until | Discontinue ACP-319 | |
| | Grade ≤1, consider systemic | permanently. | |
| Grade = 3 or 4 | corticosteroids. May resume | | |
| 014de - 3 01 4 | acalabrutinib at initial or lower | | |
| | dose level (if applicable) at | | |
| | investigator discretion. | | |
| QTC Interval Prolongation | | | |
| | | Refer to Section 4.1.9. | |
| Other Nonhematologic Adverse Events | | | |
| Grade ≤2 | Maintain current dose level | Maintain current dose level and | |

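### Section 3.8.2 requires acalabrutinib to be held for every Grade 4 toxicity, but Table 3-2 maintains it for Grade 4 neutropenia of 7 days or less and leaves it to discretion for Grade 4 hepatic events; neither table is given precedence

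*Protocol*

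**What the plan says.** **The general rule (Section 3.8.2).** "The actions in Table 3-1 should be taken for any Grade 4 toxicity or unmanageable Grade 3 toxicity". For the first and second occurrence Table 3-1 reads "Hold acalabrutinib until recovery to Grade ≤1 or baseline; may restart at" the original dose level. The third occurrence is a hold followed by restart at the reduced dose, and the fourth is discontinuation. Section 3.8.2 continues: "In addition, the actions in Table 3-1 should be taken when modification of the acalabrutinib dose is recommended for specific treatment-related AEs", with a pointer to Table 3-2.

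**The event-specific rules (Section 3.9, Table 3-2, acalabrutinib column).**
- Grade 4 neutropenia: "Maintain current dose level and schedule and monitor ANC at least 1x per week". Table 3-1 comes in only under the condition "If Grade 4 neutropenia lasts for >7 days".
- Grade 4 hepatic events: "See recommendations for" Grades 2 or 3. The Grade 3 cell reads "Withhold or continue acalabrutinib (at investigator discretion, after discussion with the medical monitor". It also allows restart at the current dose after 7 days if enzymes seem to be improving.
- Grade 4 thrombocytopenia: sent directly to Table 3-1.

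**Standing of Table 3-2.** Section 3.9 describes its contents as guidelines from which the investigator may vary. Section 3.9.2, however, says its instructions should be followed for uncomplicated hepatic laboratory abnormalities.

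**The concern.** Section 3.8.2 covers all Grade 4 toxicities and names no exception by event type or duration. A site that opens Table 3-2 for a short Grade 4 neutropenia finds the opposite instruction. The protocol's cross-references do not settle the matter. The cytopenia paragraph of Section 3.11.1 sends the reader to Section 3.8, where the hold rule stands, while Section 3.9.2 sends the reader with a hepatic abnormality to Table 3-2.

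The rules are still in use: under Amendment 6 all active subjects receive acalabrutinib monotherapy, so Table 3-1 and the acalabrutinib column of Table 3-2 govern them. The primary objective is the safety profile, and Section 3.1.1 lists AEs leading to discontinuation or dose reduction among the safety parameters. Those actions depend on how many occurrences have been counted under Table 3-1, and hence on which table a site applies.

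**Working it through.** The protocol states no figure to reproduce, so the check sets the two rules side by side for each Grade 4 event.

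1. **Neutropenia, 7 days or less.** Section 3.8.2 with Table 3-1: hold until Grade 1 or lower, or baseline. Table 3-2: no change in dose or schedule. Both cannot be followed.
2. **Neutropenia, more than 7 days.** Table 3-2 itself leads to Table 3-1. From that point there is no conflict.
3. **Hepatic event.** Section 3.8.2 with Table 3-1: hold, and restart only on recovery to Grade 1 or lower, or baseline. Table 3-2, through the Grade 3 cell: hold or continue after discussion with the medical monitor. If held, restart is possible after 7 days on signs of improvement. The restart conditions differ materially. By the grade limits in Table 3-2, an ALT that has fallen from above 20 x ULN to a value still above 5 x ULN is improving but remains Grade 3, whereas Grade 1 means 3 x ULN or less.
4. **Thrombocytopenia.** Both routes end at Table 3-1. Consistent.
5. **Diarrhea.** Both tables hold until Grade 1 or lower. They differ only in what follows: Table 3-1 permits the original dose after the first and second occurrence, while Table 3-2 says "May resume at lower dose level (if applicable) or discontinue acalabrutinib at investigator discretion". Both wordings are permissive.

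**Effect on the occurrence count.** Assume that occurrences are counted for the same event in the same subject; Table 3-1 does not say how they are counted. Take a subject with two Grade 4 neutropenia episodes of 7 days or less, followed by one lasting longer.
- Under Section 3.8.2 the long episode is occurrence 1 + 1 + 1 = 3, so restart is at the reduced dose.
- Under Table 3-2 the short episodes do not trigger Table 3-1, so the long one is occurrence 0 + 0 + 1 = 1, and restart at the original dose is permitted.

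With four short episodes, Section 3.8.2 ends in discontinuation at the fourth, and Table 3-2 triggers no dose action at all.

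**Is precedence stated anywhere?** Not in Sections 3.8, 3.8.1, 3.8.2, 3.9, 3.9.2, 3.11.1 or 3.12. Section 3.8.1 adds a further trigger, a hold for unmanageable, potentially drug-related toxicity of Grade 3 or higher, which would not by itself require a hold for a manageable Grade 4 event.

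**The case against.** The best defence is that the specific rule overrides the general one. Section 3.9 is organised by event and grade, and its neutropenia and thrombocytopenia rows say themselves when Table 3-1 applies. That suggests Table 3-2 was meant to govern listed events and Table 3-1 the rest. Section 3.8 also speaks of holding drug as necessary, and both sections ask for discussion with the medical monitor whenever possible.

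This is a plausible account of the intent, but the text does not say it. Section 3.8.2 introduces Table 3-2 with "In addition, the actions in Table 3-1 should be taken when modification of the acalabrutinib dose is recommended for specific treatment-related AEs", which makes Table 3-2 a source of further triggers for Table 3-1 and not a list of exceptions. Describing Table 3-2 as guidelines points the other way, towards Section 3.8.2 prevailing, and Section 3.9.2 then tells sites to follow Table 3-2. The medical monitor may even out practice, but only where consulted in time, and has no written order of precedence to apply.

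The defence does limit the point. A reader might infer that hepatic events also carry opposite instructions. They do not: Table 3-2 permits a hold, so the conflict is between a requirement and discretion, plus the restart condition. A reader might also count Grade 4 diarrhea as a third contradiction. Since both tables hold and both word resumption permissively, a site following Table 3-2 does not breach Table 3-1 at the first or second occurrence. That is at most a difference in wording.

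**Conclusion.** The inconsistency is real and should be corrected, within these bounds. It is a direct contradiction for Grade 4 neutropenia lasting 7 days or less. It is a lesser one for Grade 4 hepatic events, where a required hold meets discretion and the restart conditions differ. The neutropenia row alone sustains the point.

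The hepatic part rests on the Grade 3 cell. The Grade 4 cell refers to Grades 2 or 3, but the Grade 2 hepatic cells are blank in the copy read here, possibly through loss in text conversion, and should be checked in the source document.

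The effect on the safety results is indirect. Section 3.1.1 counts AEs leading to dose reduction or discontinuation, not holds, so a short neutropenia reaches those summaries only through the third and fourth occurrence. A reader might infer that relative dose intensity brings the conflict into the primary safety endpoint. The protocol does not support this: relative dose intensity is described under study treatment administration (Section 5.4.3) and is not among the safety parameters. The protocol gives no rates of Grade 4 neutropenia or hepatic events on acalabrutinib, so no number of affected subjects can be stated.

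**What to change.** Reconcile Section 3.8.2 and Table 3-1 with the Grade 4 neutropenia and Grade 4 hepatic rows of Table 3-2, and add a sentence to Section 3.8.2 saying which table takes precedence for events covered by both. Confirm at the same time that the Grade 2 hepatic cells are filled in, and check whether the resumption wording for Grade 4 diarrhea is meant to differ. Which instruction is right is for the sponsor's medical team to decide.

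The cost is one sentence and edits to a few table cells. No new data, visits or procedures are needed.

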3.9 MANAGEMENT OF SPECIFIC AEs

Recommendations for modifications of the dosing regimens based on the drug and the type and severity of AEs or laboratory abnormalities are provided in Table 3-2. The recommendations provided in Table 3-2 comprise only guidelines; variations from these recommendations may be warranted based on an investigator's individual judgment in considering potential risks, benefits, and therapeutic alternatives available to each subject. Whenever possible, any interventions for potential treatment-related AEs should be discussed between the investigator and the medical monitor before implementation.

Please refer to Section 4.1.9 for dose modifications based on QTc AEs.

Table 3-2. Recommendations for Acalabrutinib and ACP-319 Dose Modifications Based on Type and Severity of Treatment-Related Adverse Events or Laboratory Abnormalities

| Recommendation | | | | | |
|----------------------------------------------------------------------------------|--------------------------------------------------------------------------------------------------------------------------------------------------------------------------------------------------------------------------------------------------------------------|--------------------------------------------------------------------------------------------------------------------------------------------------------------------------------------------------|--|--|--|
| NCI CTCAE Grade | Acalabrutinib | ACP-319 | | | |
| Gastrointestinal Inflammation/Diarrhea | | | | | |
| Grade 1 Mild diarrhea: Increase of < 4 stools per day over baseline | Provide antidiarrheal (e.g., loperamide) and maintain current acalabrutinib dose level and schedule. Provide antidiarrheal (e.g., loperamide). Withhold acalabrutinib until Grade <1. | Provide antidiarrheal (e.g., loperamide) and maintain current ACP-319 dose level and schedule. Provide antidiarrheal (e.g., loperamide) and maintain current ACP-319 dose level and | | | |
| Grade 2 Moderate diarrhea: Increase of 4–6 stools per day over baseline | Resume acalabrutinib at current dose level. If rechallenge results in recurrence, may resume at initial or lower dose level at investigator discretion (if applicable). Consider addition of anti-inflammatory (e.g., sulfasalazine, budesonide). | schedule. Monitor at least weekly until resolved. Consider addition of anti-inflammatory (e.g., sulfasalazine, budesonide). | | | |
| Grade 3 Severe diarrhea: Increase of ≥7 stools per day over baseline | Provide antidiarrheal (e.g., loperamide). Withhold acalabrutinib until Grade ≤1. Resume at lower dose level (if applicable). Consider addition of anti-inflammatory (e.g., sulfasalazine, budesonide). | Provide antidiarrheal (e.g., loperamide). Withhold ACP-319 until Grade ≤1. Resume at lower dose level (if applicable). Consider addition of anti-inflammatory (e.g., sulfasalazine, budesonide). | | | |
| Grade 4 Life-threatening diarrhea | Provide antidiarrheal (e.g., loperamide). Withhold acalabrutinib until Grade ≤1. May resume at lower dose level (if applicable) or discontinue acalabrutinib at investigator discretion. Consider addition of anti-inflammatory (e.g., sulfasalazine, budesonide). | Discontinue ACP-319 permanently. | | | |
| Hepatic Adverse Events (elevations in ALT, AST, or bilirubin) | | | | | |
| Grade 1 (ALT/AST ≤3 x ULN) (Bilirubin ≤1.5 x ULN) | Maintain current dose level and schedule. Monitor ALT, AST, ALP, and bilirubin at least 1x per week. | Maintain current dose level and schedule. Monitor ALT, AST, ALP, and bilirubin at least 1x per week. | | | |
| Grade 2 (ALT/AST >3-5 x ULN) (Bilirubin >1.5- ≤ 3 x ULN) | | | | | |

Table 3-2. Recommendations for Acalabrutinib and ACP-319 Dose Modifications Based on Type and Severity of Treatment-Related Adverse Events or Laboratory Abnormalities

| | Recommendation | |
|-------------------------------------------------------------|------------------------------------------------------------------------------------------------------------------------------------------------------------------------------------------------------------------------------------------------------------------------------------------------------------|-------------------------------------------------------------------------------------------------------------------------------------------------------------------------------------------------------------------------------------------------------------------------------------------------------------------------------------------------------------------------------------------------------------------------------------------------------------------------------------------|
| NCI CTCAE Grade | Acalabrutinib | ACP-319 |
| Grade 3 (ALT/AST >5-20 x ULN) (Bilirubin >3-10 x ULN) | Withhold or continue acalabrutinib (at investigator discretion, after discussion with the medical monitor). Monitor ALT, AST, ALP, and bilirubin at least 1x per week. After 7 days if hepatic enzymes appear to be improving and acalabrutinib was withheld, restart acalabrutinib at current dose level. | Withhold ACP-319. Monitor ALT, AST, ALP, and bilirubin at least 1x per week until all abnormalities have returned to Grade ≤1. Recommend treating with high dose oral or IV corticosteroids (at a dosage of 40 mg prednisone or equivalent QD) for at least 48 hours; when all abnormalities have returned to Grade ≤1, recommend tapering steroids over no <4 weeks. Once abnormalities have returned to Grade ≤1, ACP-319 may resume at initial or lower dose level (if applicable). |
| Grade 4 | See recommendations for | Discontinue ACP-319 |
| (ALT/AST >20 x ULN) | Grades 2 or 3 | permanently. |
| (Bilirubin >10 x ULN) | | |
| | | diffuse interstitial pattern or |
| ground-glass opa | cities on chest CT and no d | |
| Grade 1 | Maintain current dose level and schedule. Consider pneumocystis prophylaxis. | Discontinue ACP-319 permanently. |
| Grade 2 | Withhold acalabrutinib until Grade ≤1, consider systemic corticosteroids and pneumocystis treatment. May resume at initial or lower dose level (if applicable) at investigator discretion. | Discontinue ACP-319 permanently. |
| Grade ≥≥3 | Withhold acalabrutinib until Grade ≤1, consider systemic corticosteroids and consider pneumocystis treatment. May resume at lower dose level (if applicable) or discontinue acalabrutinib at investigator discretion. | Discontinue ACP-319 permanently. |

Table 3-2. Recommendations for Acalabrutinib and ACP-319 Dose Modifications Based on Type and Severity of Treatment-Related Adverse Events or Laboratory Abnormalities

| Recommendation | | | | | |
|-----------------|-----------------------------------------------------------------------------------------------------------------------------------------------------------------------------------------------------------------------------------------------------------------------------------------|-------------------------------------------------------------------------------------------------------------------------------------------------------------|--|--|--|
| NCI CTCAE Grade | Acalabrutinib | ACP-319 | | | |
| | Neutropenia | | | | |
| Grade ≤2 | Maintain current dose level and schedule. | Maintain current dose level and schedule. | | | |
| Grade 3 | Maintain current dose level and schedule. | Maintain current dose level and schedule. Monitor ANC at least 1x per week. | | | |
| Grade 4 | Maintain current dose level and schedule and monitor ANC at least 1x per week. If Grade 4 neutropenia lasts for >7 days (neutrophil growth factors are permitted per ASCO guidelines [Smith et al. 2015b] and use must be recorded on the CRF), modify dose as instructed in Table 3-1. | Withhold ACP-319. Monitor ANC at least 1x per week until ANC ≥0.5 x 10 ⁹ /L, then resume ACP-319 at lower dose level (if applicable). | | | |
| | Thrombocytopenia | 1 | | | |
| Grade ≤2 | Maintain current dose level and schedule. | Maintain current dose level and schedule. | | | |
| Grade 3 | If no significant bleeding, maintain current dose level and schedule. In the presence of significant bleeding, modify dose as instructed in Table 3-1. | Maintain current dose level and schedule. Monitor PLT at least 1x per week. | | | |
| Grade 4 | Modify dose as instructed in Table 3-1. | Withhold ACP-319. Monitor PLT at least 1x per week until PLT ≥25 x 10 ⁹ /L, then resume ACP-319 at lower dose level (if applicable). | | | |
| | Rash | T | | | |
| Grade 1 | Maintain current dose level and schedule. | Maintain current dose level and schedule. | | | |
| Grade 2 | Maintain current dose level and schedule. | Withhold ACP-319 until Grade ≤1, consider systemic corticosteroids. May resume ACP-319 at initial or lower dose (if applicable) at investigator discretion. | | | |

Protocol: ACE-LY-001

Table 3-2. Recommendations for Acalabrutinib and ACP-319 Dose Modifications Based on Type and Severity of Treatment-Related Adverse Events or Laboratory Abnormalities

| | Recommendation | | |
|-------------------------------------|-----------------------------------|---------------------------------|--|
| NCI CTCAE Grade | Acalabrutinib | ACP-319 | |
| | Withhold acalabrutinib until | Discontinue ACP-319 | |
| | Grade ≤1, consider systemic | permanently. | |
| Grade = 3 or 4 | corticosteroids. May resume | | |
| 014de - 3 01 4 | acalabrutinib at initial or lower | | |
| | dose level (if applicable) at | | |
| | investigator discretion. | | |
| QTC Interval Prolongation | | | |
| | | Refer to Section 4.1.9. | |
| Other Nonhematologic Adverse Events | | | |
| Grade ≤2 | Maintain current dose level | Maintain current dose level and | |
| Grade SZ | and schedule. | schedule. | |
| | Withhold acalabrutinib until | Withhold ACP-319 until | |
| | Grade ≤1. May resume | Grade ≤1. May resume | |
| | acalabrutinib at initial or lower | ACP-319 at lower dose level (if | |
| Grade = 3 or 4 | dose level (if applicable) or | applicable) or discontinue | |
| Grade = 3 or 4 | discontinue acalabrutinib at | ACP-319 at investigator | |
| | investigator discretion. | discretion. If toxicity recurs | |
| | | upon rechallenge, discontinue | |
| | | ACP-319 permanently. | |

Abbreviations: ALP = alkaline phosphatase; ALT = alanine aminotransferase; ANC = absolute neutrophil count; ASCO = American Cancer Society; AST = aspartate aminotransferase; CRF = case report form; CT = computed tomography; CTCAE = Common Terminology Criteria for Adverse Events; IV = intravenous; NCI = National Cancer Institute; PLT = platelet count; QD = once daily; ULN = upper limit of normal.

